3.2. Clinical Validation Acceptance Criteria

The study results will be reported in 2×2 tables to calculate the estimated positive and negative percent agreements with the comparison device/method. Wilson two-sided 95% confidence intervals will also

Clinical Validation of the Aptitude Medical Systems Metrix COVID/Flu Test for Detection of SARS-CoV-2 and Influenza A/B in Point-of-Care and At-Home/Non-Laboratory Settings Protocol Version: 0

Protocol ID: TP-23-003

be constructed for the positive percent agreement and negative percent agreement statistics. The study will also report participant demographics and invalid test results. Success criteria are defined as a PPA \geq 95% (lower bound 95% CI \geq 85%) and an NPA \geq 98% (lower bound 95% CI \geq 95%).

4. Good Clinical Practices (GCP), Ethical Considerations, and Administrative Issues

4.1. Study Oversight

Each enrollment site may be subject to monitoring or auditing to ensure that study procedures are being appropriately followed and records have been maintained according to requirements. Data collected during the study must be provided to the Study Monitor on a regular basis (at least monthly or at the discretion of the Sponsor) and will be reviewed for accuracy and consistency. At the discretion of the Sponsor, this protocol may be prematurely terminated. Reasons may include, but are not limited to, meeting enrollment minimum requirements and acceptance criteria, new regulatory pathway information, business and/or market information/changes.

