Clinical Validation of the Aptitude Medical Systems Metrix COVID/Flu Test for Detection of SARS-CoV-2 and Influenza A/B in Point-of-Care and At-Home/Non-Laboratory Settings Protocol Version: 0

Protocol ID: TP-23-003

Protocol Title: Clinical Validation of the Aptitude Medical Systems Metrix COVID/Flu Test for

Detection of SARS-CoV-2 and Influenza A/B in Point-of-Care and Non-Laboratory

Settings

Protocol ID: TP-23-003

NCT06191393

Version 0

Date: 23 OCT 2023

Sponsor: Aptitude Medical Systems, Inc.

[name]

[name]

Sponsor Contact: [name]

Aptitude Medical Systems, Inc. Head of Scientific and Medical Affairs [contact]

[name]

[name]

CONFIDENTIALITY NOTICE:

The information contained in this document is proprietary and confidential. Any distribution, copying, or disclosure is strictly prohibited unless such disclosure is required by federal regulations or state law. Persons to whom the information is disclosed must know that it is confidential and that it may not be further disclosed by them.

The Metrix COVID/Flu Test is intended for 510(k)/De Novo submission. FOR INVESTIGATIONAL USE ONLY and has not been FDA cleared/market authorized The performance characteristics of this product have not been established.

Protocol ID: TP-23-003

1. Protocol Summary

Protocol Title	Clinical Validation of the Aptitude Medical Systems Metrix COVID/Flu Test for Detection of SARS-CoV-2 and Influenza A/B in Point-of-Care and At-Home/Non-Laboratory Settings	
Investigational Device(s)	Metrix COVID/Flu Test Metrix Reader (Gen 2)	
Primary Objective(s)	To evaluate the clinical performance (Positive Percent Agreement, Negative Percent Agreement, and 95% confidence intervals) of the Metrix COVID/Flu Test in detecting SARS-CoV-2, Influenza A, and Influenza B compared to an FDA-cleared comparator assay.	
Primary Endpoint(s)	For each target: • PPA ≥95% (lower bound 95% CI ≥85%) • NPA ≥98% (lower bound 95% CI ≥95%)	
Study Design and Procedures	This is a multi-site, prospective, cross-sectional study. Enrollment will occur in an "all-comers"/sequential manner after written informed consent (and/or verbal assent, in the case of minors) and confirmation of eligibility.	

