	All standard-of-care specimens will be collected prior to any study specimens. Participants will be asked to complete a self-test (or assisted for those under 14 years) using the investigational devices. Participants will execute all steps necessary to complete the test, including result interpretation, without any guidance or aid from study coordinators.	
	After testing with the investigational devices, a healthcare professional will collect a nasopharyngeal swab specimen for comparator assay analysis by an external reference laboratory. Comparator results will not be provided to participants.	
	Results from the investigational device will not be used to make patient healthcare decisions. Healthcare management will be determined by the healthcare provider and their patient without any involvement of the Sponsor.	
Study Population	Individuals aged 2+ years with signs and symptoms of respiratory infection. Intended users of the investigational device include lay-users (OTC/home use) with no prior laboratory experience with the investigational device. Participants aged 14 years and up will perform self-testing and participants below 14 years will be assisted by an adult.	

Protocol ID: TP-23-003

Number of Participants	Enrollment and testing will continue until a minimum of 500 negative specimens, 50 positive SARS-CoV-2 specimens, 50 positive Flu A specimens, and 30 positive Flu B specimens are collected.	
Inclusion/Exclusion Criteria	 Inclusion Criteria: Participant or guardian understands and is able and willing to provide written informed consent, and assent where applicable, prior to study enrollment. Male or female aged 2 years or older Participant is currently exhibiting fever, or one or more symptoms of respiratory tract infection (such as, but not limited to, chills, cough, shortness of breath or difficulty breathing, fatigue, new loss of taste or smell, sore throat, congestion or runny nose, nausea or vomiting or diarrhea). Participant must still be exhibiting symptoms on the day of specimen collection. Participant or guardian agrees to read, and is able to read with understanding, the AN swab QRI prior to beginning the operation of each of the Metrix COVID/Flu Test. Participant or guardian is able and willing to contribute the required swab specimens for testing and understands and is able and willing to sign the study informed consent. Exclusion Criteria:	

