	 Participant does not understand and/or is not able and willing to sign the study informed consent and/or assent. Participant or guardian is not able to comply with nasal swab collection requirements following the QRI. Participant has previously provided a specimen for the study. Participant is not able to tolerate specimen collection. Participant is currently undergoing antiviral treatment such as baloxavir marboxil (trade name Xofluza®), oseltamivir (Tamiflu®), zanamivir (Relenza®), and peramivir (Rapivab®). Participant is currently underoing, and/or has undergone within the past 30 days, treatment with prescription medication to treat novel Coronavirus SARS-CoV-2 infection, which may include but is not limited to Remdesivir (Veklury), Paxlovid, molnupiravir or receiving convalescent plasma therapy for SARS-CoV-2. Participants who have had a nasal wash or aspirate as part of their standard of care treatment on day of study visit prior to the study specimen collection. 	
Study Sites	The study will be conducted at a minimum of three investigational sites located within the United States. Additional sites may be added to the study to meet minimum subject/specimen enrollment requirements and geographic prevalence of respiratory virus	

Protocol ID: TP-23-003

	infections. This may include utilizing one or more investigational sites outside of the US (at which participants are required to be fluent in English), depending on enrollment needs and geographical/seasonal prevalence of respiratory virus infections. This study will be conducted in simulated home environments set up within or near clinical settings (e.g., urgent care clinics).
Study Duration	The study is to take place during the 2023 respiratory season. The estimated length of the specimen collection and testing phase is expected to be up to 24 weeks with an additional 2 to 3 weeks of study preparation and 2 weeks of final study closeout. Therefore, the total estimated study duration is up to 29 weeks. If the prevalence for any of the candidate analytes is low (such that enrollment targets are not met), the study may be extended into the next respiratory season to facilitate collection of additional specimens.

2. Reference Documents

1. Premarket Validation Recommendations for Developers of SARS-CoV-2 Molecular Single Analyte In Vitro Diagnostic Tests and Multi-Analyte Molecular Respiratory Panels that Include SARS-CoV-2 (Feb 2021)

3. Statistcal Analysis

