3.1. Clinical Performance Analysis

For each target, the following analysis will be performed to obtain a measure of clinical performance of the Metrix COVID/Flu Test versus the FDA-cleared comparator assay. Positive Percent Agreement (PPA) and Negative Percent Agreement (NPA) will be calculated as shown below. The PPA and NPA will be presented in separate 2x2 tables for each target with comparator vs investigational test (test device).

		Comparator Test		
		Positive	Negative	
Test	Positive	А	В	
Device	Negative	С	D	

Positive percent agreement = $100\% \times A/(A+C)$ Negative percent agreement = $100\% \times D/(B+D)$

The two-sided 95% Confidence Interval (CI) will be calculated using the Wilson Score method.

The study will also report participant demographics, percentage of invalid test results and investigational test performance on days from symptom onset (if applicable).

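### Section 4.1 lets the sponsor end the study once the acceptance criteria are met, so closure may depend on Metrix agreement, while the Wilson bound assumes one analysis at a fixed count

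*Combined protocol and SAP*

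**What the plan says.** **Closure.** Section 4.1 (Study Oversight) states: "At the discretion of the Sponsor, this protocol may be prematurely terminated". It continues: "Reasons may include, but are not limited to, meeting enrollment minimum requirements and acceptance criteria". Regulatory and business reasons follow, and the list is open-ended.

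**Meaning of acceptance criteria.** The term is the heading of section 3.2, which requires PPA of at least 95% with a lower 95% limit of at least 85%, and NPA of at least 98% with a lower limit of at least 95%. The Protocol Summary applies these to each target.

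**Counts.** The Number of Participants row begins: "Enrollment and testing will continue until a minimum of 500 negative specimens". It goes on to at least 50 SARS-CoV-2, 50 Flu A and 30 Flu B positives. No maximum is given. Collection is estimated at up to 24 weeks, and the Study Duration row adds: "If the prevalence for any of the candidate analytes is low (such that enrollment targets are not met), the study may be extended".

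**Access to results.** Section 4.1 says: "Data collected during the study must be provided to the Study Monitor on a regular basis". The stated purpose is review for accuracy and consistency. Section 4.4 sends coded test results to the sponsor without limiting when. Comparator results are withheld from participants; no similar restriction on the sponsor is described.

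**Analysis.** Section 3.1 says: "The two-sided 95% Confidence Interval (CI) will be calculated using the Wilson Score method". Section 3.2 uses 2×2 tables "to calculate the estimated positive and negative percent agreements with the comparison device/method". Neither section says when, or how many times, this is done, and neither mentions looks or an adjustment.

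**The concern.** Whether the acceptance criteria are met can be known only by cross-tabulating Metrix and comparator results. If that knowledge can inform the decision to close, the final count is no longer independent of the result. The Wilson limit in section 3.1 is a fixed-sample limit: its nominal level, one-sided 2.5% for the lower end of a two-sided 95% interval, assumes that the count was not chosen because the result had become favourable.

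At stake is how a reported pass should be read. From the plan alone, a reader of the submission could not tell whether a PPA and its lower bound came from one planned analysis or from the first favourable look. Flu B is the exposed target. At its minimum of 30 positives a single discordant result fails the criterion, and a few more concordant positives would reverse that.

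**Working it through.** The plan states no power, error rate or interim schedule, so there is no figure of its own to reproduce.

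**Inputs from the plan.** Minimums of 30 (Flu B), 50 (SARS-CoV-2, Flu A) and 500 (negatives); the two-part criteria of section 3.2; the Wilson two-sided 95% interval of section 3.1.

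**Assumptions.** The look schedules and maximum counts are mine, because the plan gives none. The true value is set at the lower-bound limit (PPA 85%, NPA 95%), where the nominal one-sided level is 2.5%.

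**Step 1: smallest passing counts.** With p = x/n and z = 1.96, the Wilson lower limit is

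[p + z²/2n − z·√(p(1−p)/n + z²/4n²)] / (1 + z²/n).

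- 29/30: (0.9667 + 0.0640 − 0.0907)/1.1281 = 83.3%, fail. 30/30: 88.6%, pass.
- 32/33: 84.7%, fail. 33/34: (0.9706 + 0.0565 − 0.0801)/1.1130 = 85.1%, pass.
- 47/50: 83.8%, fail. 48/50: 86.5%, pass.
- NPA: 490/500 meets the 98% estimate and has a lower limit of 96.4%, pass.

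So Flu B at the minimum passes only at 30/30, but 29/30 followed by four concordant positives passes.

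**Step 2: one analysis at the minimum.**

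- Flu B: 0.85³⁰ = 0.0076, or 0.8%.
- SARS-CoV-2 or Flu A: P(X ≥ 48 | n = 50, 0.85) = 1.4%.
- NPA: P(X ≥ 490 | n = 500, 0.95) = 0.05%.

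All are below 2.5%, so one look at the minimums adds no error.

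**Step 3: Flu B, continuing after a miss and closing at the first pass.** Two cases can be done by hand.

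- Looks at 30 and 34: pass with 30/30, or with 29/30 and then four concordant results. 0.85³⁰ + 30 × 0.15 × 0.85²⁹ × 0.85⁴ = 0.0076 + 4.5 × 0.004686 = 0.0287, or 2.9%.
- Looks at 30 and 40 (39/40 needed): 0.0076 + 4.5 × 0.85³⁹ = 0.0076 + 4.5 × 0.001767 = 0.0156, or 1.6%.

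The other schedules use the same exact binomial recursion, removing passing paths at each look:

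| Flu B looks (true PPA 85%) | Chance of passing |
|---|---|
| 30 only | 0.8% |
| 30, 40 | 1.6% |
| 30, 60 | 2.0% |
| every 10 to 60 | 2.8% |
| 30, 34 | 2.9% |
| 30, 45 | 3.0% |
| 30, 45, 60 | 3.4% |
| every positive, 30 to 60 | 4.4% |

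**Step 4: how much is due to looking.** Binomial discreteness moves the level even with one fixed count. At n = 34, 0.85³⁴ + 34 × 0.15 × 0.85³³ = 0.0040 + 0.0239 = 0.0279, or 2.8%, the highest of all fixed counts from 30 to 60. Against that benchmark, schedules giving 2.8% to 3.0% show little or no excess. Only the denser ones (3.4%, 4.4%) clearly exceed it.

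**Step 5: the other criteria.** SARS-CoV-2 or Flu A, with a look after every positive from 50 to 100: 2.2%. NPA, with looks from 500 to 1000: about 0.05%. The point-estimate requirement restrains both.

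**The case against.** The strongest defence is that the harm needs a step the document never states. Section 4.1 gives reasons to end the study, and it joins the minimums to the acceptance criteria, so stopping for that reason falls at or above the minimums. Sections 3.1 and 3.2 describe one set of tables and no interim analysis. The regular data review is for accuracy and consistency, and low prevalence is the only stated ground for extension.

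Much of this stands. A reader might infer that the sponsor plans to keep enrolling a failing target until it passes, or that the joined wording itself authorises this. The document supports neither. Continuation is left open only because no maximum is set. The low-prevalence condition governs extension into the next season and does not limit enrollment past a minimum within the season.

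Two objections to the size also stand. Ending the protocol would most naturally require every criterion for every target to be met together, so the per-target figures are upper bounds. A reader might also quote the much larger pass probabilities that arise at a true PPA of, say, 90%. Those are not error rates at any limit the plan sets, because its lower-bound limit is 85%.

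The defence does not remove the clause itself. It makes agreement results a reason for closure, and nothing elsewhere masks the sponsor or fixes a single analysis after closure.

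**Conclusion.** The point holds in limited form. The plan permits closure to depend on Metrix agreement, sets no maximum count, and pairs this with an unadjusted fixed-sample interval. It does not state that repeated looks will occur.

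Any numerical consequence depends on continuing after a miss and on the assumed schedule. Flu B alone can exceed the nominal 2.5%, by at most 1.9 percentage points (4.4% − 2.5%) under the densest schedule examined; the excess may be small or nil under sparser ones. The other PPA criteria and NPA stay below 2.5%. The main reason to act is interpretability: the plan should make clear that the reported bounds come from one analysis whose timing did not depend on the result. It should be fixed, with moderate confidence.

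**What to change.** Three short wording changes:

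1. **Section 4.1:** delete the reference to acceptance criteria from the reasons for termination, and add: *No decision to stop, close or extend enrollment will use Metrix agreement results.*
2. **Number of Participants row:** state that enrollment closes on comparator-positive and comparator-negative counts, or on the calendar limit or another protocol reason unrelated to agreement. Closing on counts alone would conflict with the duration provisions and with the regulatory and business reasons that section 4.1 keeps.
3. **Section 3.1:** state that PPA and NPA are computed once, after closure, on all specimens with valid paired results, with invalid results reported as already planned.

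If the sponsor wants to be able to continue after a missed criterion, the alternative is to prespecify the looks, a maximum count per target and an adjusted bound.

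The wording changes add no participants. The cost is that the sponsor gives up the option to stop or extend on an interim agreement result. They also leave the Flu B minimum as it is: closing at exactly 30 positives still requires 30/30, which is a separate sample-size matter.

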4.2. Institutional Review Board (IRB) Approval

This protocol will be reviewed by an approved central or local institutional review board (IRB) prior to the start of the study. A copy of the IRB approval(s) will be maintained by the study Sponsor and each participating study site Principal Investigator prior to and during the study.

4.3. Informed Consent and Withdrawal

Participant participation is voluntary. Participants must provide written consent (and verbal assent, in the case of minors) as part of the informed consent process. The Investigator will ensure that each study participant, or thier legally acceptable representative, is fully informed about the nature and objectives of the study and possible risks of participation prior to signing the ICF. Consent may be obtained electronically in accordance with local requirements. The Investigator will retain the original of each signed ICF.

Participants may be withdrawn from the study by any of the following mechanisms:

- Voluntary withdrawal by the participant at any time.
- Determination by the Investigator that withdrawal is in the best interest of the participant.
- Determination by the Sponsor that withdrawal is in the best interest of the participant or study.
- Determination after review that the participant was not eligible for the study.

All data collected from enrollment until withdrawal will be retained and used. Data may be collected from participants who voluntarily withdraw before completing specimen collection. All specimens will be collected, retained, and used unless the participant withdraws or is withdrawn for any reason. Participants who withdraw or are withdrawn may be replaced.

4.4. Confidentiality and Specimen/Data De-Identification

The identity of study participants and collected information will remain confidential. All study participants and associated specimens including demographic and test result information will be

Clinical Validation of the Aptitude Medical Systems Metrix COVID/Flu Test for Detection of SARS-CoV-2 and Influenza A/B in Point-of-Care and At-Home/Non-Laboratory Settings Protocol Version: 0

Protocol ID: TP-23-003

identified by a Study Participant ID code. All participant confidential identifiers will be removed from study specimens and the integrity of all protected health information (PHI) will be maintained in accordance with the IRB approved informed consent form. Only coded test results with minimal clinical information will be provided to the Sponsor. Investigational results (candidate assay) will not be made part of the participant's medical record.

4.5. Participant Risks and Benefits

Collection of upper respiratory swab specimens represents minimal risk to each participant but may cause some discomfort and/or minor bleeding.

There are no personal benefits to the study participants for participation in the study other than the knowledge gained by the Sponsor to help develop a new diagnostic test.

4.6. Protocol Deviations

The protocol described for this study will only be changed or altered on the express written approval of the PI, Study Manager, Sponsor, and IRB (when applicable).

4.7. Safety

4.7.1. Adverse Event (AE)

An adverse event is any unanticipated medical occurrence, unintended disease or injury or any untoward clinical signs (including any abnormal medical finding) in participants, users, or other persons whether or not related to the investigational medical device.

4.7.2. Serious Adverse Device Effect (SADE)

Adverse device effect that has resulted in any of the consequences characteristic of a serious adverse event.

4.7.3. Unanticipated Serious Adverse Device Effect (USADE)

Unanticipated adverse device effect is any serious adverse effect on health or safety, any lifethreatening problem or death caused by, or associated with, a device, if that effect, problem, or death was not previously identified in nature, severity, or degree of incidence in the application; or any other unanticipated serious problem associated with a device that relates to the rights, safety, or welfare of participants or users of the investigational medical device.

A serious adverse device effect which by its nature, incidence, severity or outcome has not been identified in the current version of the risk analysis report.

4.7.4. Adverse Event Reporting Requirements

The Investigator will report all Serious Adverse Events to the Sponsor within 24 hours of discovery and must be followed by a report within 10 days. Reports can be sent via email to the sponsor contact listed at the start of this protocol. The AE must also be reported to the Investigator's IRB.
